## 7.0 Methods

### 7.1 Observation period

From the start of treatment with Adcetris until the completion of 16 cycles [3 weeks per cycle]

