#### 7.4 Completion and submission of the case report form

For all patients requiring the completion of the case report form, the investigator will complete the case report form during the period from the start of treatment with Adcetris until the end of Cycle 4 and within 1 month after the end of Cycle 16, and submit it to the representative of Takeda.

If treatment with Adcetris is discontinued for any reason before the end of the observation period, the investigator will complete the case report form within 1 month after the completion of required observation submit it to the representative of Takeda. If treatment with Adcetris is discontinued due to any adverse event, however, the investigator will continue to observe the patient after treatment discontinuation until the adverse event resolves or improves wherever possible, and then complete the case report form and submit it to the representative of Takeda.

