### b) Infections

It is expected that Adcetris is used in patients who are immunocompromised due to prior treatment or the prior disease or those who are complicated with infection, and the incidence of infections is likely to be high. Therefore, the profile of infections in Japanese patients as an adverse event of particular interest (i.e., the incidence and temporal relationship with the onset of neutropenia/lymphopenia) will be determined.

c) Neutropenia

It is expected that Adcetris is used in patients with decreased neutrophil count due to prior treatment, which may increase the risk of infection and result in a high incidence of infection/severe infection. It is important to control the neutrophil count to allow for continuation of treatment (including dose reduction and restart of treatment after treatment interruption) in terms of the prevention of infection. Therefore, the profile of neutropenia in Japanese patients as an adverse event of particular interest will be determined (i.e., the status of treatment with Adcetris and neutrophil count control will be assessed and information useful for continuation of treatment with Adcetris will be collected).

d) Infusion reactions

Infusion reactions are characteristic of monoclonal antibody preparations, the profile of infusion reactions in Japanese patients as an adverse event of particular interest (including the status of premedication and the percentage of patients using premedication to prevent infusion reactions [use/non-use of premedication to prevent infusion reactions]) will be determined.

e) Pulmonary disorders

The occurrence of pulmonary disorders in Japanese patients receiving monotherapy with Adcetris as an adverse event of particular interest will be determined.

3) When to collect outcome measure data

From the start of treatment with Adcetris until the completion of 16 cycles (or upon discontinuation of treatment with Adcetris)

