Specific action taken to Adcetris	Dose reduction, treatment interruption (treatment delay), treatment discontinuation, or not provided

(3) Figure/table number

Tables 5.9.3-1 to 5.9.3-3

5.9.4 Outcome of peripheral nerve disorders (\geq CTCAE Grade 3) considered related to Adcetris by action taken with Adcetris

(1) Analysis sets to be used

Patients included in safety evaluation and patients included in safety evaluation (Hodgkin’s lymphoma) or patients included in safety evaluation (anaplastic large-cell lymphoma) who experience peripheral nerve disorder (\geq CTCAE Grade 3) considered related to Adcetris

(2) Data to be analyzed

For peripheral nerve disorders considered related to Adcetris, patients will be stratified into the categories below for each outcome and the incidence of these peripheral nerve disorders will be calculated. If the same patient has multiple occurrences of peripheral nerve disorder, the total number of occurrences will be calculated per category (for example, if the same patient has one episode of peripheral nerve disorder requiring dose reduction and one episode of peripheral nerve disorder leading to treatment discontinuation, these episodes of peripheral nerve disorder will be counted once for each category).

For each data item, missing data will be handled as “not provided.” The percentage of peripheral nerve disorders for each category will be calculated using the total number of peripheral nerve

disorders for each category as the denominator:

Data item	Category
Action taken to Adcetris	No action taken or action taken in response to the event or not provided
Specific action taken to Adcetris	Dose reduction, treatment interruption (treatment delay), treatment discontinuation, or not provided

(3) Figure/table number

Tables 5.9.4-1 to 5.9.4-3

5.9.5 Occurrence of infections considered related to Adcetris by presence or absence of drugs used for the prevention of infection

(1) Analysis sets to be used

Safety analysis set, safety analysis set (Hodgkin's lymphoma), and safety analysis set (anaplastic large-cell lymphoma)

(2) Data to be analyzed

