5.9.9 Outcome of neutropenia considered related to Adcetris by action taken with Adcetris

(1) Analysis sets to be used

Patients included in safety evaluation and patients included in safety evaluation (Hodgkin’s lymphoma) or patients included in safety evaluation (anaplastic large-cell lymphoma) who experience neutropenia considered related to Adcetris

(2) Data to be analyzed

For neutropenia considered related to Adcetris, patients will be stratified into the categories below for each outcome and the incidence of neutropenia will be calculated. If the same patient has multiple occurrences of neutropenia, the total number of occurrences will be calculated per category (for example, if the same patient has one episode of neutropenia requiring dose reduction and one episode of neutropenia leading to treatment discontinuation, these episodes of neutropenia will be counted once for each category). The percentage of neutropenia for each category will be calculated using the total number of neutropenia for each category as the denominator.

For each data item, missing data will be handled as “not provided.”

Data item	Category
Action taken to Adcetris	No action taken or action taken in response to the event or not provided
Specific action taken to Adcetris	Dose reduction, treatment interruption (treatment delay), treatment discontinuation, or not provided

(3) Figure/table number

Tables 5.9.9-1 to 5.9.9-3

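### SAP 5.9.4 tabulates neuropathy outcome by action taken, but follow-up of the event depends on the action, so the comparison can be biased (5.9.9 and Supplemental SAP 2, 2.1.3 to a lesser extent)

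*SAP*

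**What the plan says.** **The tables.** The first SAP in the file, which covers the final analysis, has two tables of event outcome by action taken. In 5.9.4 (related neuropathy of Grade 3 or higher), "patients will be stratified into the categories below for each outcome and the incidence of these peripheral nerve disorders will be calculated". In 5.9.9 (related neutropenia), "patients will be stratified into the categories below for each outcome and the incidence of neutropenia will be calculated". Supplemental SAP 2, section 2.1.3, repeats the neutropenia table with febrile neutropenia added to the event definition. The categories are no action, dose reduction, interruption or delay, discontinuation, and not provided. Percentages are taken over all events in the category. No assessment time, censoring rule or follow-up time is given.

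**Follow-up of events.** Protocol 7.4 has three cases:
- Treatment runs its course: the form is due "within 1 month after the end of Cycle 16".
- Treatment ends early for any reason: the form is due "within 1 month after the completion of required observation". The length of that observation is not defined.
- Treatment ends because of an adverse event: "the investigator will continue to observe the patient after treatment discontinuation until the adverse event resolves or improves wherever possible". No maximum or minimum is set.

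Protocol 9.2.5 adds two things. Item 3) ends adverse event collection at 16 cycles or at discontinuation. Item 1) asks for further follow-up, where possible, of events whose outcome is unresolved or unknown and whose causality cannot be evaluated, whatever action was taken.

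**The concern.** The action taken helps to set how long the outcome is watched. An event that led to stopping is, where possible, followed until it reaches a favourable outcome. An event managed while treatment continues is cut off at a date that has nothing to do with the event. Final outcomes from these two schemes are then set side by side.

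The comparison matters because Protocol 9.2.5, item 2) a) and c), wants the neuropathy and neutropenia data to inform whether and how treatment can be continued. A larger resolved share in the discontinuation column could be read as evidence on continuing versus stopping when it reflects only longer follow-up.

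**Working it through.** The plan gives no figure for these tables, so there is none to reproduce. The question is how far unequal follow-up alone can move the resolved share.

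**Inputs from the documents**
- Routine observation: 16 cycles × 3 weeks = 48 weeks (Protocol 7.1), or 336 days, matching the last closed onset band in SAP 5.2.1.
- Extension after stopping for an adverse event: open-ended (Protocol 7.4).

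**Assumptions (not in the documents)**
- Time to resolution is exponential with median m weeks, the same for every action, so there is no true difference.
- Events in continuing patients start uniformly over weeks 0 to 48 and are watched to week 48, an average of 24 weeks.
- Events that led to stopping are watched for L weeks after onset.

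**Formulas**
- Stopped: share resolved = 1 − 2^(−L/m).
- Continuing, averaged over onset: 1 − [m/(48 ln 2)] × [1 − 2^(−48/m)].

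Example, m = 12. Continuing: 12/(48 × 0.6931) = 0.3607; 0.3607 × (1 − 0.0625) = 0.338; 1 − 0.338 = 66.2%. Stopped with L = 26: 1 − 2^(−26/12) = 77.7%.

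| Median m (weeks) | Continuing | Stopped, L = 4 | L = 12 | L = 26 | L = 52 | L = 104 |
|---|---|---|---|---|---|---|
| 1 | 97.0% | 93.8% | 100.0% | 100.0% | 100.0% | 100.0% |
| 2 | 94.0% | 75.0% | 98.4% | 100.0% | 100.0% | 100.0% |
| 12 | 66.2% | 20.6% | 50.0% | 77.7% | 95.0% | 99.8% |
| 26 | 43.6% | 10.1% | 27.4% | 50.0% | 75.0% | 93.8% |
| 52 | 26.1% | 5.2% | 14.8% | 29.3% | 50.0% | 75.0% |

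**Differences, stopped minus continuing, with no true effect**
- m = 12, L = 26 to 104: 77.7 − 66.2 = +11.5 points, up to 99.8 − 66.2 = +33.6.
- m = 26, same range: 50.0 − 43.6 = +6.4, up to 93.8 − 43.6 = +50.2.
- m = 1 and 2, L = 26 or more: 100 − 97.0 = +3.0 and 100 − 94.0 = +6.0.
- m = 12, short follow-up: 50.0 − 66.2 = −16.2 at L = 12, and 20.6 − 66.2 = −45.6 at L = 4.

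**Sensitivity to selection.** If events that lead to stopping resolve at half the rate of the others (m = 26 for the others), the stopped column shows 29.3% at L = 26, 50.0% at L = 52 and 75.0% at L = 104, against 43.6%. Selection of more persistent events can cancel or reverse the effect.

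**The case against.** Several points against the concern have force.

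- A reader might infer that only events leading to discontinuation get extra follow-up. That is not so. The rule in Protocol 9.2.5, item 1), applies whatever the action, and the SAP counts as related every event the investigator did not rule out, so such events enter these tables. The rule is narrow, since both conditions must hold, and it does not equalise the columns.
- A reader might infer that stopping is bound to look better. The documents do not support that. The 7.4 extension applies only where possible and has no minimum. An early event in a continuing patient can have nearly 48 weeks of observation. The sign reverses with short follow-up after stopping or with selection of persistent events.
- It is tempting to set 60 days of remaining observation against 365 days after stopping, which at a 90-day median gives 37% versus 94% resolved. Neither length is in the documents. With onset uniform over 336 days, the first figure becomes 1 − [90/(336 × 0.6931)] × [1 − 2^(−336/90)], about 64%.
- Follow-up under 7.4 may end at improvement, and SAP 5.2.1 separates recovering from recovered. The calculation models resolution only, so it illustrates the mechanism and does not forecast the table.
- The tables are descriptive, with no test or confidence interval, and the listings in SAP 5.10 and 5.11 show onset and outcome dates per patient. This helps a careful reader, but the listings do not correct the summary percentages.

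What stands is that follow-up differs by action and the tables neither adjust for it nor say so.

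**Conclusion.** The point holds as a possible bias, not a certain one. SAP 5.9.4 compares outcomes across actions whose follow-up is set partly by the action and, for events that led to stopping, partly by the outcome. For slow-resolving Grade 3 or higher neuropathy the bias probably favours discontinuation. Under equal resolution rates, onset uniform over 48 weeks and 26 to 104 weeks of follow-up after stopping, it is about +12 to +34 points for a 12-week median and +6 to +50 points for a 26-week median. It reverses if follow-up after stopping is short. For 1- to 2-week medians it is about 3 to 6 points, so if neutropenia resolves that fast, 5.9.9 and Supplemental SAP 2, 2.1.3 are a minor matter. The documents give no resolution times, onset pattern or actual follow-up after stopping, so direction and size cannot be settled from them. Nor do they support reading the tables as a planned test of stopping against continuing.

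**What to change.** In SAP 5.9.4, and as a minor point in 5.9.9 and Supplemental SAP 2, 2.1.3:

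1. Add outcome by action at a common time after onset, for example resolved or improved by day 84, from the onset and outcome dates already collected. Show unresolved events not followed that long as not evaluable, in their own row; dropping them would inflate the resolved share.
2. Show median follow-up after onset for each action category.
3. Footnote the final-outcome table: follow-up differs by action, and the table does not support comparing actions. The common time point equalises follow-up but does not remove selection of worse events into stopping.
4. If time to resolution is analysed, start the clock at the date of the action or use a landmark. Curves from onset grouped by eventual action build in immortal time. Censor at the last date the event was assessed: the final observation date (Protocol 9.2.4.3) is recorded after 16 cycles or at discontinuation and may not cover the 7.4 extension.

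Protocol 7.4 and the two rules in 9.2.5 should also be reconciled on how long event outcomes are followed.

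The cost is SAP wording and one extra table per event type, with some events not evaluable at the later time point.

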5.9.8 Treatment with Adcetris at the onset of neutropenia considered related to Adcetris

(1) Analysis sets to be used

Patients included in the safety analysis set and safety analysis set (Hodgkin’s lymphoma) or safety analysis set (anaplastic large-cell lymphoma) who experience neutropenia considered related to Adcetris

(2) Data to be analyzed

For each CTCAE Grade (the worst one) of neutropenia considered related to Adcetris, patients will be stratified into the categories below, and the incidence of events of neutropenia will be calculated. If the same patient has multiple occurrences of neutropenia, the total number of occurrences will be calculated per category (for example, if the same patient has one episode of peripheral nerve disorder requiring dose reduction and one episode of peripheral nerve disorder leading to treatment discontinuation, these episodes of peripheral nerve disorder will be counted once for each category). The percentage of neutropenia for each category will be calculated using the number of neutropenia for each CTCAE grade (the worst one) as the denominator.

For each data item, missing data will be handled as “not provided.”

Data item	Category
Action taken to Adcetris	No action taken or action taken in response to the event or not provided
Specific action taken to Adcetris	Dose reduction, treatment interruption (treatment delay), treatment discontinuation or not provided

(3) Figure/table number

Tables 5.9.8-1 to 5.9.8-3

5.9.9 Outcome of neutropenia considered related to Adcetris by action taken with Adcetris

(1) Analysis sets to be used

Patients included in safety evaluation and patients included in safety evaluation (Hodgkin’s lymphoma) or patients included in safety evaluation (anaplastic large-cell lymphoma) who experience neutropenia considered related to Adcetris

(2) Data to be analyzed

For neutropenia considered related to Adcetris, patients will be stratified into the categories below for each outcome and the incidence of neutropenia will be calculated. If the same patient has multiple occurrences of neutropenia, the total number of occurrences will be calculated per category (for example, if the same patient has one episode of neutropenia requiring dose reduction and one episode of neutropenia leading to treatment discontinuation, these episodes of neutropenia will be counted once for each category). The percentage of neutropenia for each category will be calculated using the total number of neutropenia for each category as the denominator.

For each data item, missing data will be handled as “not provided.”

Data item	Category
Action taken to Adcetris	No action taken or action taken in response to the event or not provided
Specific action taken to Adcetris	Dose reduction, treatment interruption (treatment delay), treatment discontinuation, or not provided

(3) Figure/table number

Tables 5.9.9-1 to 5.9.9-3

5.9.10 Occurrence of infusion reaction considered related to Adcetris

(1) Analysis sets to be used

Safety analysis set, safety analysis set (Hodgkin’s lymphoma), and safety analysis set (anaplastic large-cell lymphoma)

(2) Data to be analyzed

The incidence of infusion reaction considered related to Adcetris for each CTCAE grade (the worst one) will be calculated by infusion reaction and PT (see Section 1.2 for the definition of infusion reaction). For infusion reactions, the number and percentage of patients with infusion reaction will be calculated. For PT, the number and percentage of infusion reactions will be calculated. PTs will be presented in ascending order or PT Code.

The CTCAE grade (the worst one) is higher in the order of Grades 5, 4, 3, 2, 1, and unknown. If the same patient has multiple occurrences of infusion reaction or there are multiple occurrences of the same PT, the highest CTCAE grade (the worst one) for the patient or PT will be counted once for the category:

Data item	Category
CTCAE Grade (the worst one) of infusion reaction	Grade 1, Grade 2, Grade 3, Grade 4, Grade 5, or unknown

(3) Figure/table number

Tables 5.9.10-1 to 5.9.10-3

5.9.11 Occurrence of the new onset of infusion reaction observed within 2 days after treatment with Adcetris and considered related to Adcetris (time of the new onset)

(1) Analysis sets to be used

Patients included in safety evaluation and patients included in safety evaluation (Hodgkin's lymphoma) or patients included in safety evaluation (anaplastic large-cell lymphoma)

(2) Data to be analyzed

The incidence of the new onset of infusion reaction observed within 2 days after treatment with Adcetris and considered related to Adcetris will be calculated by time of onset. In addition, similar calculation will be performed by use or non-use of premedication to prevent infusion reaction. See the table below for the categories of time of onset:

Data item	Category
Time of onset	During infusion of Adcetris, after the completion of infusion of Adcetris (≤ 1 hour, >1 hour to ≤ 12 hours, >12 hours to ≤ 24 hours, >24 hours), or unknown

(3) Figure/table number

Tables 5.9.11-1 to 5.9.11-3

5.9.12 Occurrence of infusion reaction observed within 2 days after treatment with Adcetris and considered related to Adcetris by use or non-use of premedication to prevent infusion reaction

(1) Analysis sets to be used

Safety analysis set, safety analysis set (Hodgkin's lymphoma), and safety analysis set (anaplastic large-cell lymphoma)

(2) Data to be analyzed

The total number of doses of Adcetris^{*1} will be calculated by use or non-use of premedication to prevent infusion reaction (absent, present, or unknown). In addition, the incidence of infusion reaction observed within 2 days of the most recent treatment with Adcetris (i.e., observed on the day of treatment or on the day after treatment with Adcetris) and considered related to Adcetris will be calculated for each CTCAE grade (the worst one). The CTCAE grade (the worst one) is higher in the order of Grades 5, 4, 3, 2, 1, and unknown. If the same patient has multiple occurrences of infusion reaction during the same period, the one with the highest CTCAE grade (the worst one) will be counted once^{*2}.

The percentage of infusion reaction by use or non-use of premedication to prevent infusion reaction will be calculated using the total number of doses of Adcetris for each of these categories (i.e., use or non-use) as the denominator.

*1: The total number of doses of Adcetris by use or non-use of premedication to prevent infusion reaction refers to the total doses per patient calculated by use or non-use of premedication. For example, if one patient receives 8 doses of Adcetris with premedication and 8 doses of Adcetris

without premedication, and another patient receives 10 doses of Adcetris with premedication and 6 doses of Adcetris without premedication, the total number of doses of Adcetris will be 18 (8 + 10) for the use of premedication and 14 (8 + 6) for the non-use of premedication.

*2: For example, if the date the most recent treatment with Adcetris is January 1, 2016 and “Grade 2” infusion reaction is observed on January 1, 2016, and “Grade 3” infusion reaction on January 2, 2016, these two episodes of infusion reaction will be counted as one episode of “Grade 3” infusion reaction.

Data item	Category
CTCAE Grade (the worst one) of infusion reaction	Grade 1, Grade 2, Grade 3, Grade 4, Grade 5, or unknown

(3) Figure/table number

Tables 5.9.12-1 to 5.9.12-3

5.9.13 Occurrence of adverse drug reactions of pulmonary disorder and infections

(1) Analysis sets to be used

Safety analysis set, safety analysis set (Hodgkin’s lymphoma), and safety analysis set (anaplastic large-cell lymphoma)

(2) Data to be analyzed

The incidence of pulmonary disorders considered related to Adcetris for each CTCAE grade (the worst one) will be calculated by pulmonary disorder and PT. PTs and PT Codes will be presented in ascending order.

In addition, the incidence of pulmonary disorders considered related to Adcetris for each CTCAE grade (the worst one) will be calculated by patient demographics and baseline characteristics.

The CTCAE grade (the worst one) is higher in the order of Grades 5, 4, 3, 2, 1, and unknown. If the same patient has multiple occurrences of pulmonary disorders or there are multiple occurrences of the same PT, the highest CTCAE grade (the worst one) for the patient or PT will be counted once for the category:

Data item	Category
CTCAE Grade (the worst one) for pulmonary disorders	Grade 1, Grade 2, Grade 3, Grade 4, Grade 5, or unknown

Items and categories of patient demographics and baseline characteristics

Data item	Category
History of or concurrent pulmonary disorder	Absent or present
Smoking history	Non-smoker or smoker * Patients other than those who have never smoked will be classified into “smoker.”
Prior radiotherapy	Absent or present

(3) Figure/table number

Tables 5.9.13-1 to 5.9.13-4

5.10 analysis setanalysis setanalysis setList of actions taken with Adcetris in patients experiencing peripheral nerve disorders considered related to Adcetris

(1) Analysis sets to be used

Patients included in the safety analysis set analysis setanalysis setwho experience peripheral nerve disorders considered related to Adcetris

(2) Data to be analyzed

(3) For each patient, a list of the following data items: patient number, diagnosis, action taken or not taken with Adcetris, reason for action taken, date of dosing and dose for each cycle, date of onset of peripheral nerve disorder, CTCAE grade (the worst one), outcome, and the date of outcome. If the

same patient has multiple occurrences of peripheral nerve disorder, all these occurrences will be counted. Figure/table number

Table 5.10

5.11 List of actions taken with Adcetris in patients experiencing neutropenia considered related to Adcetris

(1) Analysis sets to be used

Patients included in the safety analysis set analysis setanalysis setwho experience neutropenia considered related to Adcetris

(2) Data to be analyzed

For each patient, a list of the following data items: patient number, diagnosis, action taken or not taken with Adcetris, reason for action taken, date of dosing and dose for each cycle, date of onset of neutropenia, intervention provided for neutropenia, specific intervention (e.g., name of drugs/therapies) outcome, and the date of outcome. If the same patient has multiple occurrences of neutropenia, all these occurrences will be counted.

(3) Figure/table number

Table 5.11

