## 3.0 Estimated Enrollment and Its Rationale

### 3.1 Estimated enrollment

140 patients (with relapsed/refractory CD30+ Hodgkin's lymphoma or anaplastic large cell lymphoma)

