### 3.2 Rationale

It is expected that the detailed evaluation of peripheral nerve disorders, infections, neutropenia, infusion reactions, and pulmonary disorders will help better understand the safety profile of Adcetris in the routine clinical setting, which will lead to the assessment of the risk-benefit balance of the drug.

The frequencies of peripheral nerve disorders, infections, neutropenia ( $\geq$ Grade 3), infusion reaction, and pulmonary disorder in non-Japanese phase 2 studies (pooled study data from a study in patients with Hodgkin's lymphoma [SG035-0003, 102 patients] and a study in patients with systemic anaplastic large cell lymphoma [SG035-0004, 58 patients]) were 56%, 61%, 20%, 11%, and 6%, respectively.

Observation of infusion reactions with the lowest frequency of  $\geq 10$  patients, aside from pulmonary disorders, with a probability of 95% would require 140 patients, which was therefore determined to be the estimated enrollment. It is estimated that when the number of patients enrolled reaches 140 patients,  $\geq 4$  patients have adverse events of pulmonary disorder with a probability of 95%.

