	digits being 6290002 or 6290004 that are entered in the field of “Drugs used for the prevention of infection” (If more than one antifungals are used in the same patient, it will be counted as one patient.)
Antivirals	Drugs with the first three digits of YJ Code being 625 that are entered in the field of “Drugs used for the prevention of infection” (If more than one antivirals are used in the same patient, it will be counted as one patient.)
Trimethoprim-sulfamethoxazole combinations	Drugs with YJ Code being 62901000 that are entered in the field of “Drugs used for the prevention of infection” (If more than one trimethoprim-sulfamethoxazole combinations are used in the same patient, it will be counted as one patient.)
Other prophylactics against infections	Any drug entered in the field of “Drugs used for the prevention of infection” other than prophylactics against infections listed above (If more than one other prophylactics against infections are used in the same patient, it will be counted as one patient.)
Peripheral sensory neuropathy (as an adverse event)	Adverse events with “Sensory neuropathy” entered in the “Category of peripheral nerve disorders” in the field of “Adverse events: [1] Peripheral nerve disorders] in the case report form. MedDRA PT Code 10034620 should be assigned regardless of data entered in “Symptoms” in the field.
Peripheral motor neuropathy (as an adverse event)	Adverse events with “Motor neuropathy” entered in the “Category of peripheral nerve disorders” in the field of “Adverse events: [1] Peripheral nerve disorders] in the case report form. MedDRA PT Code 10034580 should be assigned regardless of data entered in “Symptoms” in the field.
Peripheral neuropathy (as an adverse event)	Adverse events with “Other” entered in the “Category of peripheral nerve disorders” in the field of “Adverse events: [1] Peripheral nerve disorders] in the case report form. MedDRA PT Code 10029331 should be assigned, regardless of data entered in “Symptoms” in the field.
Pulmonary disorders (as adverse events)	Adverse events that fall under the category of Appendix “Definition of Pulmonary Disorders”
Infusion reaction (as an adverse event)	MedDRA PT Code 10051792 (Infusion related reaction) will be assigned, regardless of symptoms entered in the field of “Adverse events: [4] Infusion reaction.”

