5.9 Analysis of items of particular interest

5.9.1 Occurrence of the adverse drug reaction of peripheral nerve disorder and infections

(1) Analysis sets to be used

Safety analysis set, safety analysis set (Hodgkin's lymphoma), and safety analysis set (anaplastic large-cell lymphoma)

(2) Data to be analyzed

The incidence of peripheral nerve disorders considered related to Adcetris will be calculated for each CTCAE grade (the worst one) by symptom of peripheral nerve disorder (peripheral sensory neuropathy, peripheral motor neuropathy, or peripheral neuropathy) and PT (see Section 1.2 for the definition of symptoms of peripheral nerve disorders). For symptoms of peripheral nerve disorders, the number and percentage of patients with peripheral nerve disorder will be calculated. For PT, the number and percentage of peripheral nerve disorder will be calculated. PTs will be presented in ascending order of PT code.

The CTCAE grade (the worst one) is higher in the order of Grades 5, 4, 3, 2, 1, and unknown. If the same patient has multiple occurrences of the same symptom of peripheral nerve disorder or the same PT, the symptom of peripheral nerve disorder or PT with the highest CTCAE grade (the worst one) will be counted for the respective category once per patient:

Data item	Category
CTCAE Grade (the worst one) for peripheral nerve disorders	Grade 1, Grade 2, Grade 3, Grade 4, Grade 5, or unknown

(3) Figure/table number

Tables 5.9.1-1 to 5.9.1-3

5.9.2 Occurrence of peripheral nerve disorders considered related to Adcetris by patient demographics and baseline characteristics and treatment given

(1) Analysis sets to be used

Safety analysis set, safety analysis set (Hodgkin’s lymphoma), and safety analysis set (anaplastic large-cell lymphoma)

(2) Data to be analyzed

For each data item of patient demographics and baseline characteristics and treatment given, patients will be stratified into the categories below, and the incidence of peripheral nerve disorders considered related to Adcetris will be calculated by CTCAE Grade (the worst one). The CTCAE grade (the worst one) is higher in the order of Grades 5, 4, 3, 2, 1, and unknown. If the same patient has multiple occurrences of the same peripheral nerve disorder (PT), the peripheral nerve disorder with the highest CTCAE grade will be counted once for the category:

Data item	Category
CTCAE Grade (the worst one) of peripheral nerve disorder	Grade 1, Grade 2, Grade 3, Grade 4, Grade 5, or unknown

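### The SAP's grouped tables for pulmonary and peripheral nerve disorders are related-only, and no table gives the all-cause number of patients with any event in either group

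*SAP*

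**What the plan says.** **Protocol.** Section 3.2 lists planning rates for peripheral nerve disorders, infections, neutropenia of Grade 3 or higher, infusion reactions and pulmonary disorders, which "were 56%, 61%, 20%, 11%, and 6%, respectively". The enrolment figure is derived from infusion reactions ("Observation of infusion reactions with the lowest frequency of" at least 10 patients). A second sentence adds that with 140 enrolled at least 4 "patients have adverse events of pulmonary disorder with a probability of 95"%. Section 9.2.5, item 2) e), says that the occurrence of pulmonary disorders "as an adverse event of particular interest will be determined". Neither place restricts the count by causality.

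**SAP definitions.** The definition table describes pulmonary disorders as "Adverse events that fall under the category of Appendix" terms, again with no causality condition. The Appendix lists 44 PTs. Neuropathy entered in the dedicated case report form field is recoded to one of three PTs: sensory, motor or other. Adverse drug reactions are all events except those the investigator called not related.

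**SAP tables.** The special-interest table for pulmonary disorders (5.9.13) reads: "The incidence of pulmonary disorders considered related to Adcetris for each CTCAE grade (the worst one) will be calculated by pulmonary disorder and PT". The one for neuropathy (5.9.1) reads: "The incidence of peripheral nerve disorders considered related to Adcetris will be calculated for each CTCAE grade (the worst one"). Sections 5.9.2 to 5.9.4 and the listing in 5.10 carry the same restriction. Events regardless of cause appear in 5.1.1, 5.2.1, 5.2.2 and 5.7, arranged by SOC and by individual PT.

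**The concern.** The protocol states its pulmonary expectation in adverse events, and the SAP defines the group as adverse events, but the only table that assembles the group drops those judged not related. The quantity the protocol names is therefore not tabulated.

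This matters because the survey has a single arm. Protocol Table 3 allows an event to be called not related when the primary disease, a concurrent illness or another therapy very likely explains it. The pulmonary Appendix includes terms such as radiation pneumonitis, hypoxia and respiratory failure, for which such explanations are plausible in this population. A related-only count depends on individual causality judgements, and it cannot fairly be set against an expectation worded in adverse events. For neuropathy the gap in the tables is the same, but the protocol attaches no expected count to that group.

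**Working it through.** **1. Can the grouped all-cause count be recovered?** In SAP 5.1.1 each PT is counted once per patient. A patient with two different PTs from the group therefore contributes to two rows, and the rows do not show which patients overlap. The number with any event in the group lies between the largest single PT row and the sum of the rows. As an illustration only: two pulmonary rows of 4 patients each are consistent with anything from 4 patients (4/140 = 2.9%) to 8 patients (8/140 = 5.7%). An SOC row does not settle it, because it is not limited to the group's terms.

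The same test on the other harms:
- Infections are defined as one SOC, so the all-cause patient count is in 5.1.1.
- Infusion reactions are coded to one PT, so the count is in 5.1.1.
- Neutropenia is one PT in the main SAP after recoding. Supplemental SAP 2 adds febrile neutropenia, so this holds for the main SAP only.
- Pulmonary disorders (44 PTs) and neuropathy (three PTs) have no combined all-cause count.

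**2. Reproducing the plan's figures.** Inputs from Protocol 3.1 and 3.2: n = 140, 11% for infusion reactions, 6% for pulmonary disorders. Formula: P(X ≥ r) = 1 − Σ C(n,k) p^k (1−p)^(n−k), summed over k = 0 to r−1.
- Infusion reactions, r = 10, p = 0.11: the smallest n with probability of at least 0.95 is 140, where P = 0.952. The enrolment figure reproduces exactly.
- Pulmonary disorders, p = 0.06: expected 140 × 0.06 = 8.4 patients; P(X ≥ 4) = 0.971 and P(X ≥ 5) = 0.927. Four is the largest count that reaches 95%, so the protocol's sentence is correct if read as at least 95%.
- Neuropathy: 140 × 0.56 = 78.4 expected. This rate enters no calculation in the rationale.

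**3. What the related-only table would show.** Assume that 6% is an all-cause rate and that a share s of those patients has an event counted as related. The documents give neither fact. Then p = 0.06 × s:

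| Share s (assumed) | p | Expected patients | P(at least 4 of 140) |
|---|---|---|---|
| 100% | 0.060 | 8.4 | 0.971 |
| 90% | 0.054 | 7.56 | 0.948 |
| 75% | 0.045 | 6.3 | 0.879 |
| 50% | 0.030 | 4.2 | 0.608 |

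**The case against.** The case on the other side has real weight.

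- A reader might infer that the basis for 140 patients is undermined. It is not. Infusion reactions set that number, and their all-cause count is available from 5.1.1. The pulmonary sentence is a by-product of 140, and the 56% is only listed.
- A reader might infer that all-cause data on these harms go unreported. They do not. Every pulmonary PT and each neuropathy PT has an all-cause count in 5.1.1, with grade in 5.2.2. Table 5.7 also shows serious events considered not related in parentheses. The SAP treats events on the sponsor's medically significant list as serious whatever the investigator says, and that list includes acute respiratory failure and interstitial pneumonia. The gravest unrelated lung events would be visible.
- A reader might infer that the SAP breaches the protocol's analysis section. Protocol 10.4 and 10.4.1 ask for frequencies by SOC and PT, and by type, onset and seriousness, which the SAP supplies. The sentence in 9.2.5 sits in the rationale for selecting events for detailed collection.
- If the phrase about relatedness in 5.9 follows the SAP's definition of adverse drug reactions, indeterminate events stay in. Only events judged not related are lost, which would push the share s towards 100%. At 90% the probability is 0.948, practically the stated 95%.
- The related-only restriction may be deliberate, and no formal comparison with 6% is planned.

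All of this limits the consequence. None of it supplies the missing count: bounds are not a patient total, and 5.7 covers serious events only.

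**Conclusion.** The point holds as a gap in reporting. The SAP has no all-cause, patient-level total for the pulmonary group or for the three neuropathy PTs combined, although the protocol describes both as adverse events of particular interest. That finding rests on the table definitions alone and needs no assumption.

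The size of the consequence is less certain. If the 6% is all-cause, the chance that the related-only table shows the expected 4 patients falls from 0.971 to 0.95, 0.88 or 0.61 at shares of 90%, 75% or 50%. These shares are illustrative, and the lowest of the three figures should not be read as a forecast. They affect only what one table displays; the events collected are the same. The argument is stronger for pulmonary disorders, where the protocol states an expected count, than for neuropathy.

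**What to change.** In SAP 5.9.13 and 5.9.1, add beside the related-only figures the all-cause number and percentage of patients with at least one event in the group (any of the 44 pulmonary PTs; any of the three neuropathy PTs), by worst CTCAE grade. A 95% confidence interval is optional. Use the all-cause row when results are set against the pulmonary expectation in Protocol 3.2, and state whether the 6% and 56% source rates are all-cause.

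The cost is SAP wording and one extra row in two existing tables, each produced for the overall, Hodgkin's and anaplastic large cell safety sets. Onset, grade and causality are already collected for every adverse event. Sample size, data collection and clinical management do not change.
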